# **Number of Subjects, Recruitment and Informed Consent**

Statistical power analysis (see below) requires a group of 25 subjects. We plan to enroll 100 evaluable subjects randomly assign into four groups; we intend to enroll 150 subjects to account for unevaluable participants. See experimental design details below. Healthy participants will be recruited by listing on UMClinicalStudies.org and by postings at area colleges and community groups in Ann Arbor. Interested volunteers will call the phone number of a designated recruiter for an initial phone screening. The initial phone screening will consist of questionnaires related to medical history, demographic information, handedness, inclusion and exclusion criteria and procedure standard MRI screening questionnaire. If interested, the participant will complete the questionnaires, which will be reviewed by the study team. The health status will be confirmed by the attending anesthesiologist before the study on site. Once eligibility is confirmed by the study team, the one-time research study session will be scheduled. Participants will screened for COVID-19 prior to entry into the hospital per hospital guidelines. A standard face mask will be provided upon hospital entry if participants do not have one.

All participants will give written informed consent according to institutional guidelines prior to any testing. The Principal Investigators or their designee will obtain consent using a written consent form approved by the Institutional Review Boards of the University of Michigan Medical School (IRBMED). It will contain detailed information regarding the purpose, risks and benefits of participating. Copies of the signed consent form will be given to the subjects; the original consent will remain with the study team. Subjects will be compensated for their involvement.

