## **Experimental Design**

Three 30-min sessions will be conducted including wakeful baseline, moderate sedation, and the application of LIFUP under moderate sedation (sedation+LIFUP) with an effect-site concentrations of 1.5 µg/ml (Fig. 2). Moderate sedation will be achieved by IV infusion of propofol to achieve effect-site concentrations of 1.5 µg/ml. Infusion rate will be manually controlled. An initial bolus dose and subsequent infusion rate for each participant will be pre-determined based on a pharmacokinetic model [26] developed for target-controlled propofol infusion and implemented in software (STANPUMP [27]). A 5-min equilibration period between baseline and moderate sedation will be included. After sedation+LIFUP session, the infusion will be terminated allowing for spontaneous recovery of consciousness. A random group assignment will be applied in four groups of participants receiving LIFUP with sham control, or in the DLPFC, AIC, or CT, respectively.

[figure not shown]
[figure not shown]

Fig. 2. Concept, design and anticipated outcomes. In the hypothetical brain process (top left) visual

information propagates through ventral (V1/V2-->VOTC) and dorsal (V1/V2-->MTG-->PPC) pathways. The AIC receives inputs from the VOTC and prioritizes the inputs before sending them to the DLPFC for global broadcasting. The activities of DLPFC and AIC are hypothetically associated with two orthogonal SDT quantities, criterion (c) and sensitivity (d'). Given the wiring of the mesocircuit and thalamocortical loops (e.g., DLPFC-CT, and AIC-CT), the CT is hypothetically associated with the product of c and d'. Experimental design (bottom left) includes three fMRI sessions: wakeful baseline, moderate sedation, and LIFUP under moderate sedation. Participants will be assigned at random to four groups: those receiving LIFUP to DLPFC, AIC, CT or sham control. Anticipated effects are illustrated (right). Abbreviations: early visual cortex (V1/V2), ventral occipitotemporal cortex (VOTC), middle temporal gyrus (MTG), posterior parietal cortex (PCC).

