**Primary Outcome Measure:** Blood Oxygen Level Dependent (BOLD) response to visual stimuli (timeframe: baseline to 90 minutes).

**Secondary Outcome Measure:** Perceptual criterion (c) and sensitivity (d') derived from the Signal Detection Theory (SDT) (timeframe: baseline to 90 minutes).

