We will calculate the average BOLD activity (across the trials with real images) in the regions of interest including the CT, AIC, and DLPFC. For a given measurement, repeated-measures ANOVA plus post-hoc tests will be performed at the group level. Inter-subject multivariate linear regression analyses will be performed with SDT metrics as dependent variables and average BOLD activity as independent variables. Statistical significance will be defined at FDR-corrected  $\alpha < 0.05$ .

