# **Power Analysis**

For an fMRI study of cognitive function, Desmond and Glover [29] reported that about 25 subjects are necessary to achieve 80% power for a 0.5% increase of activity. We also conducted power analysis based on our previous study with graded sedation of propofol [30]. The average Cohen's d as a measure of the effect size was 0.56. For 80% power and  $\alpha$ =0.05, N=24 human subjects will be needed. The obtained subject number is also very close to the suggested optimal group size for reliable statistics in functional MRI studies [31]. We plan for a minimum of 25 subjects per group.

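### The randomised LIFUP-versus-sham comparison has no specified contrast and no covariates; an ANCOVA of session 3 on the two earlier sessions would define it, with a power gain that depends on the between-session correlation

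*Combined protocol and SAP*

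**What the plan says.** The design is in Experimental Design: "Three 30-min sessions will be conducted including wakeful baseline, moderate sedation, and the application of LIFUP under moderate sedation". The first two sessions precede any sonication. The same section sets out the randomisation: "A random group assignment will be applied in four groups of participants receiving LIFUP with sham control, or in the DLPFC, AIC, or CT, respectively".

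Number of Subjects, Recruitment and Informed Consent gives the size ("We plan to enroll 100 evaluable subjects randomly assign into four groups"), with 150 enrolled to allow for unevaluable participants. Power Analysis adds: "We plan for a minimum of 25 subjects per group". I read this as 25 evaluable participants in each of four groups.

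The primary outcome is the BOLD response to visual stimuli; the secondary outcomes are c and d'. Data Analysis and Statistics takes BOLD in three regions (CT, AIC, DLPFC) and then states: "For a given measurement, repeated-measures ANOVA plus post-hoc tests will be performed at the group level". Significance is FDR-corrected at 0.05. The section does not list the ANOVA factors, say whether group is among them, name the contrast that answers LIFUP versus sham, mention a covariate for that comparison, or define the FDR family.

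**The concern.** Randomisation protects one comparison: the groups against each other in session 3. Session order is fixed, so a change from session 2 to session 3 within one arm mixes LIFUP with time under propofol, and only the sham group separates the two. The predictions in Anticipated Results and Interpretation (DLPFC stimulation moves c but not d', AIC stimulation the reverse, CT stimulation both) rest on that comparison.

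Two things are at stake. First, the stated method covers several different tests of LIFUP versus sham, and nothing says which one counts. Second, every participant contributes two measurements that treatment cannot have affected. They are natural covariates, and the plan does not use them as such. With 25 per group the between-group comparison is the weak one, so efficiency matters here.

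**Working it through.** **1. The plan's own sample size.** Power Analysis gives d = 0.56 from an earlier propofol sedation study, 80% power, alpha 0.05 and N = 24. For a within-subject comparison, n = ((1.96 + 0.842)/0.56)² = 25.03, or 26 rounded up, which is close to 24. A two-sided paired t-test needs 28 and a one-sided one 22. A two-group comparison needs 2 × 25.03 = 50.06, or 51 per group. So N = 24 fits a within-subject comparison only. The plan gives no power for a between-group contrast.

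**2. Inputs for the LIFUP contrast.** From the documents: four groups, 25 per group, three sessions, alpha 0.05. Assumed: two-sided tests without FDR adjustment, equal SD in all sessions, an effect of 0.56 SD in session 3 only (borrowed for scale; it is not a LIFUP effect), and equal correlation ρ between sessions.

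**3. One active arm against sham.** The noncentrality is 0.56/√(2v/25) on 96 df, where v is the residual variance relative to a raw session value. For unadjusted session 3 (v = 1) it is 0.56/√0.08 = 1.98, and power is 50%. For the two-covariate ANCOVA at ρ = 0.5, v = 0.5 × 2/1.5 = 0.667, the noncentrality is 2.42, and power is 67%.

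| Analysis | v | ρ = 0.3 | ρ = 0.5 | ρ = 0.7 | ρ = 0.8 |
|---|---|---|---|---|---|
| Session 3 alone | 1 | 50% | 50% | 50% | 50% |
| S3 − S2 | 2(1−ρ) | 38% | 50% | 72% | 87% |
| S3 − mean(S1, S2) | 1.5(1−ρ) | 48% | 62% | 83% | 95% |
| ANCOVA on S2 only | 1−ρ² | 54% | 62% | 78% | 90% |
| ANCOVA on S1 and S2 | (1−ρ)(1+2ρ)/(1+ρ) | 56% | 67% | 85% | 95% |

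At ρ = 0.3, 0.5 and 0.7, the two-covariate ANCOVA gains 6, 17 and 35 points over session 3 alone, 18, 17 and 14 over S3 − S2, and 8, 5 and 2 over S3 − mean(S1, S2). At ρ = 0.8 the last gain is under 1 point.

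**4. Omnibus tests, like for like.** Let one active arm have the effect. The sum of squared group deviations is 0.56² × 3/4 = 0.2352. For ANCOVA, λ = 25 × 0.2352/v = 5.88/v on 3 df. For group-by-session, λ = 25 × 0.2352 × (2/3)/(1−ρ) = 3.92/(1−ρ) on 6 df. Power at ρ = 0.3, 0.5 and 0.7 is 56, 68 and 88% for ANCOVA against 36, 51 and 76% for the interaction, a gain of about 12-19 points. At ρ = 0.8 it is about 5 points.

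**5. Unequal correlations.** For (r12, r13, r23) = (0.3, 0.3, 0.5), (0.5, 0.5, 0.5) and (0.5, 0.5, 0.7), two-covariate ANCOVA gives 63, 67 and 81%. S3 − S2 gives 50, 50 and 72%. S3 − mean(S1, S2) gives 57, 62 and 75%, which is 5-7 points below ANCOVA.

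**6. Accuracy.** The formulas ignore chance imbalance in the covariates. Simulating the scenarios in step 5 gave ANCOVA power of 62, 66 and 79%, 1-2 points lower. Gains of 1-2 points should be read as no difference.

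**The case against.** The strongest reply is that the plan does not commit to an inefficient test. It states no factors, no interaction term and no particular post-hoc contrast, and its reference to the group level may mean no more than analysis across participants. A reader might infer that the ANOVA wastes the two pre-LIFUP sessions, or that LIFUP will be judged by a 6-df interaction followed by raw session 3 or change-score tests. The documents do not support either reading. A group-by-session term uses all three sessions; they go unused only if groups are compared at session 3 alone, which the plan does not say.

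Nor is a large gain assured. A sensible repeated-measures contrast, session 3 against the mean of the earlier two, comes within 2-8 points of ANCOVA under equal correlation. Setting a 6-df omnibus test beside a 1-df pairwise contrast would exaggerate the difference. A suitably contrasted repeated-measures ANOVA is also valid under randomisation, so no bias is shown.

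Finally, replacing the ANOVA outright would leave stated hypotheses without a test. Rationale and Hypothesis and Anticipated Results and Interpretation both expect CT stimulation to restore performance to the awake level, which is a session 3 versus session 1 question. The former also expects the three targets to differ from one another.

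All of this stands, and it limits the claim. It does not supply the missing contrast, and no alternative computed beat the two-covariate ANCOVA.

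**Conclusion.** The point holds as a gap in specification with an inexpensive, efficient remedy. It does not show that the stated method is invalid. The plan does not say which test answers the randomised question and does not use the pre-LIFUP sessions as covariates.

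ANCOVA on both earlier sessions was at least as powerful as every alternative computed. Under the stated assumptions it is clearly better than the omnibus interaction, the S3 − S2 change or unadjusted session 3 at most correlations from 0.3 to 0.7, and only slightly better than the best fixed contrast. At correlation 0.8 the advantage over the other tests that use earlier sessions narrows, while that over unadjusted session 3 widens.

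The size is uncertain. The documents give no between-session correlation and no LIFUP effect size, and equal SD in awake and sedated sessions is assumed. Power after FDR correction would be lower than shown. The change should be made, but the trial does not depend on it.

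**What to change.** In Data Analysis and Statistics, for BOLD in each of CT, AIC and DLPFC, and for c and d':

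- Make the randomised comparison an ANCOVA of the session 3 value on group (four levels), with the session 1 and session 2 values as covariates.
- Report the three active-minus-sham differences and the three between-target differences with confidence intervals. That is 5 measures × 6 differences = 30 contrasts; state that they lie inside the FDR family.
- Test sedation separately as session 2 versus session 1, pooled over all participants, since the groups are treated alike until session 3. At the plan's d = 0.56, power is 77% with 25 participants and over 99.9% with 100.
- Keep a within-subject session 3 versus session 1 test for the return-to-baseline hypothesis. Do not reduce the repeated-measures ANOVA to a purely descriptive role.

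The cost is plan wording and no new data. Statistically it takes 2 error degrees of freedom (96 to 94) and a linearity assumption for the covariates.

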# **Anticipated Results and Interpretation**

We expect to observe a decrease of both c and d' during sedation, indicating more conservative responses and reduced stimulus differentiation. This would suggest that suppressing the state of consciousness diminishes the quality of conscious content. We also expect to find an overall reduction of average BOLD activity across all examined regions, i.e., in CT (state control), AIC (content gating) and DLPFC (content broadcasting). Furthermore, the change of c (baseline vs. sedation) may be associated with the change of DLPFC's average BOLD activity, and the change of d' may be associated with the change of AIC's average BOLD activity. The change of c × d' may be associated with the change of CT's average BOLD activity. Because the activity of CT supervenes on the activity of DLPFC and AIC, the state (CT) and contents (DLPFC/AIC) are altered together in sedation. If found, the results would suggest a neural mechanism for the linkage between state and contents. We also anticipate that the LIFUP stimulation in DLPFC during sedation will increase c without changing d' and increase the average BOLD activity in the

DLPFC. Stimulation of the AIC will increase d' without changing c, possibly through an enhancement of salience/attentional process offsetting the general inhibitory effect of propofol. Importantly, stimulation of the CT is expected to substantially increase both d' and c, arguably restoring perceptual performance to baseline level. This may be accompanied by an overall increase of average BOLD activity along the entire visual processing pathway.

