In this study, we aim to determine how conscious contents are degraded during anesthetic modification of the conscious state, and to disentangle the causal roles of specific brain areas in state-content interaction through a perturbational approach. We hypothesize that suppressing the state of consciousness will diminish the quality of conscious contents and that this will be associated with functional alterations in three key brain areas: CT, AIC and DLPFC. We also hypothesize that stimulating the three areas will lead to differential perceptual outcomes (e.g., a change in subjective perceptual criterion alone, detection sensitivity alone, or both).

To test the hypotheses, we will (1) administer propofol to reduce the state of consciousness (moderate sedation), (2) perform near-threshold perceptual task to assess the contents of consciousness, (3) apply transcranial low-intensity focused ultrasound pulsation (LIFUP) to noninvasively stimulate the CT, AIC and DLPFC, and (4) perform functional magnetic resonance imaging (fMRI) to measure the related brain process during baseline, sedation, and sedation+LIFUP. We will measure the quality of conscious contents by two orthogonal quantities, criterion (c) and sensitivity (d') derived from the Signal Detection Theory. Here c captures the tendency of a subject to report subjective recognition of a target stimulus regardless of whether the target is present or absent, whereas d' captures the ability of a subject to distinguish between target present and absent trials.

We anticipate that suppressing the conscious state will decrease both c and d', indicating more conservative responses and reduced stimulus differentiation, while c and d' are differentially affected by the activity of DLPFC and AIC. Furthermore, neither c nor d' alone but their product will be associated with the activity of the CT, thus implying a putative mechanism for state-content

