relationship by the functional interaction of brain areas CT for controlling state, and AIC and DLPFC for gating and broadcasting, respectively, the conscious contents. We also anticipate that stimulating the DLPFC and AIC will differentially change c and d'. Stimulating the CT will positively shift c and substantially increase d', thereby restoring perceptual performance to the awake baseline level. This will be associated with an increase of task-related activity in the DLPFC and AIC. If so, this would disentangle the causal roles of CT, AIC and DLPFC on perceptual outcomes.

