Visual task. Participants will be asked to lay in the scanner, pay attention on the screen, and complete an image recognition task. All stimuli will be programmed using E-Prime (Psychology Software Tools, Pittsburgh, PA) and delivered via a visual presentation system designed for an MRI environment. Stimuli will be presented at the threshold of subjective recognition. An adaptive thresholding procedure will be conducted whereby image contrast will be titrated to reach a 50% subjective recognition rate for each subject. Stimuli will include two common visual object categories: faces and houses. Participants' task is to report the category ("F" or "H") of an image presented and their recognition experience ("Yes" or "No") (Fig. 3). Specifically, they will be instructed to report the object category regardless of their recognition experience and, in cases of unrecognized images, to make a genuine guess (two-alternative choice discrimination). Then, they will be instructed to report whether they see an object, such that even if the object appears unclear or noisy, they should respond "yes", but if they see nothing or only low-level features, such as cloud-like abstract patterns, they should respond "no".

**Fig. 3.** Visual task design. During each 30-min session, participants will complete an image recognition task. Stimuli (faces, houses, and scrambled images) will be presented at the threshold of subjective recognition. Participants' task is to report the category ("F" or "H") of the image presented and their recognition experience ("Yes" or "No").

The stimulus set will include real and scrambled images, where the scrambled images will be created by phase-shuffling a randomly chosen real image from each category to preserve category specific low-level image features [28]. Because scrambled images do not include an object stimulus, they are used as "catch trials" to determine the subjects' baseline tendency to give positive responses to a question about their recognition experience. Each object category will include four unique real images and one scrambled image. Each image will be repeated 10 times (i.e., trials) for each 30-min session. The pre-stimulus interval will vary randomly from trial to trial between 4 and 8 seconds to prevent stimulus timing predictability. The stimuli will be presented in a randomized order to prevent category predictability.

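### The causal roles of DLPFC, AIC and CT are to be read from patterns in c and d', but no planned test compares the effect on c with the effect on d', and no margin defines unchanged or restored

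*Combined protocol and SAP*

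**What the plan says.** The section Rationale and Hypothesis expects stimulation of the three areas to produce different perceptual outcomes: "a change in subjective perceptual criterion alone, detection sensitivity alone, or both". It then says that, if the anticipated results appear, "this would disentangle the causal roles of CT, AIC and DLPFC on perceptual outcomes". Anticipated Results and Interpretation gives the pattern: "LIFUP stimulation in DLPFC during sedation will increase c without changing d" (that is, d'); "Stimulation of the AIC will increase d' without changing c"; and CT stimulation raises both, with performance arguably back at the awake level.

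Under Experimental Design, "Participants will be assigned at random to four groups: those receiving LIFUP to DLPFC, AIC, CT or sham control". Criterion c and sensitivity d' are the secondary outcome; the primary is the BOLD response.

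Data Analysis and Statistics has two sentences on group-level inference. The first is "For a given measurement, repeated-measures ANOVA plus post-hoc tests will be performed at the group level". The second is "Inter-subject multivariate linear regression analyses will be performed with SDT metrics as dependent variables and average BOLD activity as independent variables". Significance is FDR-corrected at 0.05, with the family of tests not named. No section gives a contrast between c and d', or a margin for no change or for restoration.

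**The concern.** To say that a target acts on c but not on d' is to say that two effects differ. Finding one significant and the other not does not test that difference. To say that a metric is unchanged, or back at baseline, is to say that a difference is small. Non-significance does not show that unless the interval is narrow relative to a stated margin.

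An analysis of one measurement at a time supplies neither test. The regression does take the SDT metrics together, but its predictor is BOLD activity and not stimulation group, so it cannot say what stimulating a given target did to c relative to d'. Followed as written, the plan could label a target selective when it acts equally on both metrics, and report a partial recovery as a full one.

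**Working it through.** **Inputs from the documents.** Cohen's d 0.56, 80% power, alpha 0.05, N=24, at least 25 per group (Power Analysis). Four randomised groups, one of them sham (Experimental Design). Formulas d' = Z(HR) − Z(FAR) and c = 0.5 × (Z(HR) + Z(FAR)) (Data Analysis and Statistics).

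**Assumptions.** The documents give no effect size for LIFUP on c or d', and no correlation between their changes. I use 0.56 SD of change with a range of 0.3 to 0.8, and correlation 0 with a range of −0.75 to +0.7. Tests are two-sided at 0.05, before FDR unless stated.

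**The plan's own figure.** A one-group normal calculation gives ((1.960 + 0.842)/0.56)² = 25.03, so 26; the t version gives 28 two-sided or 22 one-sided. The stated 24 is of this within-group kind. A two-group comparison at 0.56 needs 51 to 52 per group, and 25 per group gives 49% power against sham.

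**What a null result can exclude, with 25 per group.**
- Against sham: t(0.975, 48) × √(2/25) = 2.011 × 0.283 = 0.57 SD.
- Against own baseline: t(0.975, 24)/√25 = 2.064/5 = 0.41 SD of the paired difference.

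The first is as large as the planning effect and the second is not far below it.

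**How often one metric is significant and the other is not.** If both effects equal 0.56 SD and the correlation is 0, exactly one is significant with probability 2p(1−p) = 2 × 0.492 × 0.508 = 50%. This formula peaks at 50% when p = 0.5, so the plan's own size sits near the maximum for that correlation.

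Simulation (40,000 trials, 25 per arm, shared sham, 0.56 SD):

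| Result for one target | r = −0.75 | r = 0 | r = +0.3 | r = +0.7 |
|---|---|---|---|---|
| Equal effects: exactly one significant | 74% | 50% | 40% | 26% |
| Equal effects: only the predicted one | 37% | 25% | 20% | 13% |
| Truly selective: only the predicted one | 47% | 47% | 47% | 47% |
| Truly selective: c-minus-d' contrast significant | 18% | 28% | 38% | 71% |

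Over the full range of effect size and correlation:
- Exactly one significant, equal effects: about 16% to 75%.
- Only the predicted metric significant: 8% to 37% if effects are equal, 16% to 76% if truly selective. The odds in favour of selectivity are about 1.9 to 1 in the central case, with a range of 0.9 to 8.4.
- Predicted metric and c-minus-d' contrast both significant: about 2% (1% to 3%) if equal and 24% (7% to 77%) if selective. The odds are about 10 to 1 (3 to 29). If the scaling SD is estimated from the same sample, the 2% becomes about 3% and the odds about 8 to 1.
- False double dissociation (DLPFC on c only, AIC on d' only): 2% to 7%, or 1% to 5% after FDR, at 0.56 SD and correlation −0.75 to +0.3.

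**Where a negative correlation could come from.** "Each object category will include four unique real images and one scrambled image". With two categories and ten repetitions, each session has 2 × 4 × 10 = 80 real and 2 × 1 × 10 = 20 scrambled trials. With V = p(1−p)/(nφ²), where φ is the normal density at Z(p), trial error alone gives Corr(c, d') = (V_HR − V_FAR)/(V_HR + V_FAR). For assumed hit rates of 0.3 to 0.5 and false-alarm rates of 0.1 to 0.3 this is −0.60 to −0.76. True variation between subjects dilutes it. For example, independent true variation with SD 0.5 in the change in d' and 0.25 in the change in c (assumed values) moves −0.76 to about −0.43.

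**The case against.** The strongest reply has four parts.

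1. Anticipated Results and Interpretation is worded as expectation, and c and d' are secondary. This limits the weight of the point. It does not remove it, because Rationale and Hypothesis draws the causal conclusion from the pattern.

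2. A reader might infer that the plan leaves its sham arm unused. The documents do not support that. With four randomised groups and three sessions, a group-by-session ANOVA with sham comparisons is the natural reading, and its absence from the text is a matter of wording. Nor is it right that c and d' are never analysed together; the regression does so, against BOLD.

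3. A reader might infer that the trial will probably announce a false dissociation, or that 50% is a general error rate. Neither follows. The causal conclusion depends on the whole pattern, and a false DLPFC/AIC double dissociation is rare. The 50% depends on a borrowed effect size that happens to put power near one half; at zero correlation it is about 30% at 0.3 SD and 33% at 0.8 SD. After FDR over the six active-versus-sham tests, the 0.56 SD figure is 37% (29% to 58% for correlations of +0.3 to −0.75).

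4. A reader might also infer that the 80/20 trial split forces c and d' apart. It may push that way, but the size rests on assumed response rates and counts trial error only.

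The lack of any comparison between the two effects, and of any margin, stands after all four.

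**Conclusion.** The point holds as a gap between the conclusions the plan intends and the tests it specifies. It should be corrected, but it does not affect the primary outcome. The core is logical and needs no simulation: no planned test compares the effect on c with the effect on d', and at 25 per group a non-significant result cannot rule out an effect of about the planning size against sham.

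The simulated size depends on assumptions. In the central case, a result in which only the predicted metric is significant favours true selectivity by less than 2 to 1; adding the contrast raises this to roughly 8 to 10 to 1. The 0.56 comes from an earlier propofol sedation study and is not stated to apply to c, d' or LIFUP, so the ranges matter more than the central figures.

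**What to change.** In Data Analysis and Statistics, state:

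1. LIFUP effects on c and d' are the group-by-session contrasts, active against sham, reported with 95% confidence intervals.
2. A target is called selective for c or d' only if its effect on the predicted metric is significant and its contrast of standardised change in c minus d', against sham, is also significant. Fix the standardising scale in advance.
3. DLPFC and AIC are said to differ only on the direct contrast: DLPFC minus AIC on c, minus the same on d'.
4. Non-significant results are worded as no change shown, or difference from baseline not shown, unless the interval lies inside a margin fixed in advance.

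**Cost.** No new data and no change of procedure, but selectivity claims become harder to reach, and the plan should say so. Rule 2 has about 24% power at 0.56 SD and correlation 0, or about 13% after FDR over eight contrasts (six active-versus-sham, two c-minus-d'). For 80% power the c-minus-d' contrast alone would need about 102 per group at correlation 0. Rule 3 fares better if the predictions are exactly right: the contrast is then 2 × 0.56 = 1.12 SD, or 1.12/√2 = 0.79 in its own SD units, with 78% power at correlation 0 (54% at −0.76). A claim of no change against sham is hard to support at this size: an equivalence test (two one-sided tests at 0.05, true difference zero) has 26% power at a margin of 0.56 SD, and 80% power needs a margin of about 0.83 SD. For most null results, the cautious wording is what the data will support.
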